Canada has made notable progress in the promotion of booster seat use. Specifically, Canada's automobile research program has produced new booster seats that are easy to carry and install, as well as attractive to school age children.¹¹ Furthermore, nine provinces have now enacted laws mandating booster seat use,¹² and evidence-based education programs have been developed and implemented throughout the country.^{13–15} Despite these advances, new approaches to encourage booster seat use are required, because legislation has proven insufficient to effectively promote booster seat use.^{16–18} For example, in 2010, more than 10 years after booster seats became mandatory in Ontario and Quebec, the rate of utilization in each of the two provinces was only 25%.⁵ Furthermore, recent research indicates that parents' perception of the safety benefit of boosters seats is the single, strongest predictor of use,^{19,20} yet no study to date has tested an education intervention that increases perceived benefit.^{21–34} Instead, studies conducted to date focus on teaching guidelines (i.e., minimum and maximum age, height, and weight to determine when a child should use a booster seat, and when it is safe for a child to use only the seatbelt).

My approach to encouraging booster seat use is novel, because I propose that, in addition to learning guidelines, parents need to understand two principles: (1) seatbelts prevent injuries by redirecting crash forces to stronger parts of the body (hips and chest); and (2), without booster seats, children would wear the seatbelt on their abdomen and neck, which directs crash forces to more vulnerable anatomical structures (internal organs and spine). Once parents grasp these two principles, they will appreciate the safety benefit of booster seats and, thus, will be more likely to use them.

Background

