Intervention. The intervention will be the enhanced Transport Canada booster seat material that was developed in the previous phase. The intervention material will be the same as the one for the control group in all respects (font size, formatting, etc.), except that it will contain an introduction explaining, in plain language: (a) seatbelts redirect crash forces to the child's thorax and pelvis; (b) booster seats ensure children wear the seatbelt correctly across the hips and chest; and (c) booster seats, used in combination with the seatbelts, prevent injuries to head, neck, spine, abdomen, internal organs, as well as injuries resulting from ejection. The final version of these introduction and accompanying figures will be decided, based on input from the focus groups.

Outcome measures. The primary outcome measures are perceived safety benefit of booster seats and intention to use them, as assessed by the Booster Seat Attitudes Scale (BSAS).²⁰ The BSAS has been validated and tested in a Canadian sample of parents, and the Benefit and Intent subscales of the BSAS reported good internal consistency (Cronbach's alpha of 0.85 and 0.84, respectively). Secondary outcome measures are information recall (when it is safe to start using a booster seat, how to install it, how to use it, and when it is safe for a child to use only the seatbelt) and self-efficacy (as measured by the Perceived behavioural control subscale of the BSAS; Cronbach's alpha of 0.87), their subjective estimates of the risk reduction afforded by booster seats (from 0 to 100%), their subjective estimate of the impact of the intervention on other parents, time they spend reading the material, clicks on links to additional booster seat information.

UPDATE 27 OF JUNE 2019: Factor validation of the BSAS revealed that using the Benefit subscale actually comprises Perceived Benefit (i.e., understanding that booster seats prevent injuries) and Key Benefit (i.e., understanding that booster seats prevent life threatening injuries to the spine and abdomen). Similarly, the Intent subscale of the BSAS was found to have factors: Intent to Use and Intent to Learn (i.e., intention to attend a car seat clinic or workshop). The projected intent scale, developed for this study also had two factors: Projected intent to use and projected intent to learn. These new subscales constitute the updated outcome measures.

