After pilot-testing is complete, participants will be recruited through an online market research firm, Maru/Matchbox, which maintains a nationwide panel of 130,000 individuals whose distribution represents the Canadian population. Maru/Matchbox will send an email invitation to participate along with a link to the online survey. The landing page of the survey will provide description of the study for parents to read. The online survey will be set up in such a way that participants won't be able to start answering questions, unless they consent by clicking the "I

agree" button. Participants, will be advised to print and keep a copy of the consent form either as PDF or as hard copy. After consenting to participate, the online trial will proceed as follows:

- 1. Participants will complete a demographics questionnaire, the BSAS, and four questions on booster seat guidelines (e.g., minimum and maximum ages, heights, and weights to determine when a child should use a booster seat, and when it is safe for a child to use only the seatbelt).
- 2. The system will randomly assign the participant to either the intervention or the control group. Randomization will be stratified by sex, child age, and jurisdiction to ensure both groups are equal. This stratification is necessary because, in Canada: (a) fathers and mothers differ in their attitudes regarding child vehicle safety,⁴⁵ (b) booster seat use decreases as the child gets older,⁴⁶ and (c) provinces differ from one another in terms of legislation and booster seat education programs.⁴⁷
- 3. Participants in the intervention group will be presented the enhanced booster seat material, while participants in the control group will be presented the current Transport Canada booster seat material. Material provided to both groups will be stripped of logos (Transport Canada logos and corporate identity), but will be properly cited.
- 4. Participants will complete again the BSAS and the questions on booster seat guidelines.
- 5. Participants in the intervention group will be asked one or two multiple choice questions to ensure they did not misunderstood the information in an unintended way. These questions will be designed based on the information on adverse effects collected during the focus groups and the trial's pilot. If a parent answers incorrectly, the system will clarify the information immediately after.

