- 6. Participants in the control group will be given the option to view the enhanced booster seat material, in order to give them the opportunity to benefit from the intervention.

Analysis. The online version of the Booster Seat Attitudes Scale will be factor-validated and Cronbach's alpha of each BSAS subscale will be calculated to determine reliability. The effect of the intervention on the Benefit, Intention, and Self-Efficacy subscales of the BSAS will be examined through linear mixed effects models with random effects by province (to account for between-province differences in legislation and booster seat education programs). Multiple imputation will be used to address missing data. Intention-to-treat analysis will be conducted, by doing two separate analyses: one with the entire sample of participants and one with only participants who complete the trial. In addition, mediation analysis will be conducted to determine if perceived safety benefit mediated the effect of the intervention on intent to use booster seats. Dropout curves will be used to examine in which part of the trial participants in each condition were more or less likely to drop out. *Student's t, Wilcoxon Sign and Rank*, or *Mann-Whitman's U* tests will be used to compare, across groups, subjective estimates of the impact of the intervention on other parents, time spent reading the material, number of clicks on links to additional booster seat information, and pre- versus post-intervention difference in subjective estimates of the risk reduction afforded by booster seats and by seatbelts.

UPDATE 27 OF JUNE 2019:

Increase in perceived safety benefit of booster seats (primary outcome) and increase in intention to use booster seat (a secondary outcome) were evaluated by, first calculating the difference between the post-intervention score and the pre-intervention score for each participant. This difference was then compared with t tests (two-tailed). Parents' judgments of the impact of the intervention on their peers (a secondary outcome), which was assessed post-intervention only, was compared across study arms with the t tests (two-tailed). The same statistical analysis was used to evaluate the other secondary outcomes (parents' recall of booster seat information, Interest in booster seat information).

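### The recall analysis should adjust for the Step 1 guideline answers and report an interval; the planned t test is valid but makes poorer use of the baseline

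*Combined protocol and SAP*

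**What the plan says.** The Outcome measures section lists recall among the secondary outcomes: "Secondary outcome measures are information recall", covering when to start with a booster seat, how to install and use it, and when the seatbelt alone is safe.

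Under Setting and Procedures, Step 1 collects the BSAS and "four questions on booster seat guidelines" before randomisation. Step 4, after the material, reads: "Participants will complete again the BSAS and the questions on booster seat guidelines". A before and an after value therefore exist for each parent who completes the trial.

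The Analysis paragraph that precedes the update names no method for recall. The update of 27 June 2019 describes two analyses in turn. Benefit and intention are compared by two-tailed t tests on post-minus-pre differences. Judged impact on peers, "which was assessed post-intervention only, was compared across study arms with the t tests (two-tailed"), is compared on the post value. The next sentence begins "The same statistical analysis was used to evaluate the other secondary outcomes" and names recall and interest in booster seat information in brackets. No recall score, confidence interval or margin is given.

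**The concern.** The arms read the same material, which in the intervention arm is identical "except that it will contain an introduction explaining, in plain language" how belts and boosters protect the child. The rationale is that, "in addition to learning guidelines, parents need to understand two principles". A reader of the results will therefore want to know what the added text did to guideline recall, in either direction. Recall is the only listed outcome that measures guideline knowledge directly in both arms; the comprehension questions in Step 5 go to the intervention arm only.

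Two things weaken the answer.

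- **Precision.** On the natural reading, what parents already knew at Step 1 stays in the comparison as noise, although it was measured.
- **Reporting.** The update describes a test and no interval. A bare non-significant p-value is easily taken as reassurance that nothing was lost, especially as the Knowledge Translation section foresees quick uptake by agencies.

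**Working it through.** **Inputs from the documents.** Participants and Budget: 606 completed surveys. Ethical considerations: half the participants are not exposed to the intervention during the trial, so 606/2 = 303 per arm. (The Participants section's 303 mothers and 303 fathers is a split by parent, not by arm.)

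**Assumptions, not in the documents.** Recall is scored 0-4 from the four guideline questions; SD 0.8-1.2, equal before and after; pre/post correlation r = 0.5 or 0.7; two-sided 5% level.

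**The plan's own figure.** No figure is given for recall. The 606 was set for 0.4 points on the Benefit subscale, without SD, alpha or power, so it cannot be reproduced. At two-sided 5% it would correspond to an SD of about 1.76 (80% power) or 1.52 (90%).

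**Formulas for the 95% half-width.**

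- Post-only t test: 1.96 × SD × √(2/303), with √(2/303) = 0.0812
- Change-score t test: post-only × √(2(1−r)), a factor of 1.000 at r = 0.5 and 0.775 at r = 0.7
- Adjusted for Step 1: post-only × √(1−r²), a factor of 0.866 at r = 0.5 and 0.714 at r = 0.7

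**Results, in questions.**

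| SD | Post-only | Change, r=0.5 | Change, r=0.7 | Adjusted, r=0.5 | Adjusted, r=0.7 |
|---|---|---|---|---|---|
| 0.8 | 0.127 | 0.127 | 0.099 | 0.110 | 0.091 |
| 1.0 | 0.159 | 0.159 | 0.123 | 0.138 | 0.114 |
| 1.2 | 0.191 | 0.191 | 0.148 | 0.165 | 0.136 |

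**Gain expressed as sample size.**

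- Against post-only: 1/(1−r²) = 1.33 at r = 0.5 and 1.96 at r = 0.7, so 33% to 96% more parents.
- Against change scores: 2(1−r)/(1−r²) = 2/(1+r) = 1.33 and 1.18, so 33% and 18% more.

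**What the planned test can see.** For a true loss of 0.25 question, the standard error is SD × 0.0812 = 0.065, 0.081 and 0.097. Power is Φ(0.25/SE − 1.96): about 97%, 87% and 73% for SD 0.8, 1.0 and 1.2.

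**What a non-significant result leaves open.** In SD units, a true loss of 0.10, 0.15 or 0.20 SD would be non-significant about 77%, 54% and 31% of the time. An estimate just short of significance in the direction of a loss gives an interval reaching about 2 × 0.159 = 0.32 SD.

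**The case against.** Most of the case on the other side stands, and it limits the point.

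- **Validity.** A reader might infer that a post-only comparison is biased, or that it is the reason a loss cannot be excluded. Neither is so. Under randomisation it is unbiased, and a change-score or adjusted test reported only as a p-value has the same limit. Ignoring Step 1 costs precision.
- **Sensitivity to a loss.** A reader might infer that the planned analysis would miss a loss. The test is two-tailed and, under the assumptions above, would flag a quarter-question loss with 73-97% power. Only smaller losses would often go undetected.
- **Aim.** The trial's objective is superiority on perceived benefit and intention. The documents nowhere claim that recall is preserved, nor say that a non-significant result will be read that way. That extra text crowds out the guidelines is conjecture. The explanation of belt position could even help recall of how to use the seat, and the final introduction was left to the focus groups.
- **Wording.** Because recall is asked twice, the update could mean a t test on change. That Step 1 is unused is the natural reading, not a certainty.

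What survives is that, on either reading, adjusting for Step 1 is at least as precise in large samples and uses data the procedures already collect.

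**Conclusion.** The point holds as an improvement in precision and reporting for a secondary outcome. It is neither an internal contradiction nor a threat to the primary result. Against a post-only test the gain is equivalent to 33-96% more parents at correlations of 0.5-0.7; against a change-score test it is 33% falling to 18%. On the assumed 0-4 scale the half-width falls from 0.13-0.19 to 0.11-0.17 or 0.09-0.14 of a question. The relative gains depend only on the correlation, given equal variances before and after; the absolute widths also depend on the assumed score, SDs and 303 completers per arm.

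A reader might go further and conclude that recall needs a formal non-inferiority test. The documents do not support that: they set no such hypothesis and give no basis for a tolerable loss. An interval conveys what can and cannot be excluded without one.

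**What to change.** In the June 2019 update, replace the reference back to another outcome's analysis with an explicit statement for recall:

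1. Define the recall score and say which questions enter it.
2. Compare the Step 4 score between arms in a linear model with the Step 1 score as covariate, and report the adjusted arm difference with its 95% confidence interval.
3. If the difference is not significant, state the largest loss the interval leaves open, and do not describe the result as showing that guideline learning is preserved.

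No margin is required. Since the update is written in the past tense, any margin named now should be labelled post hoc. If the t test result is already known, show it beside the adjusted estimate and date the change.

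The cost is two or three sentences and one regression on data the procedures already collect. Step 1 precedes randomisation, so the covariate should be available for nearly every randomised parent. The one drawback is that a statement of no difference in recall may have to be worded more cautiously.
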